## 7.4 Retesting and Rescreening

### 7.4.1 Retesting

Retesting is defined as repeating laboratory tests within the same Screening Period.

Subjects who initially fail to qualify for the study based on laboratory test results may be retested once for each laboratory parameter within the 4-week Screening Period, per investigator discretion.

### 7.4.2 Rescreening

Subjects who fail to qualify for the study based on laboratory tests may be considered for rescreening at the discretion of the investigator if it is considered that the subject status has changed, and the subject may now qualify for the study. Additionally, subjects who fail to qualify for the study based on inclusion criteria values for TSAT, ferritin, folate, or B12 values may be considered for rescreening after receiving replacement therapy.

Screening is limited to 3 attempts (initial Screening and 2 additional rescreening attempts). A new informed consent is required to be signed prior to every rescreening.

## 7.5 Study Completion, Study Termination, and Individual Site Termination

### 7.5.1 Study Completion

The study will be considered completed after all randomized subjects have completed their final study visit (Visit 15/Week 24), Safety Follow-Up or Early Termination).

### 7.5.2 Study Termination

The sponsor may terminate this study prematurely, either in its entirety or at any study site, for reasonable cause provided that written notice is submitted in advance of the intended termination. Advanced notice is not required if the study is stopped due to safety concerns. If a study site has been suspended or terminated, prompt notification will be given to investigators, IRBs, and regulatory authorities in accordance with regulatory requirements. Criteria and

procedures for premature study termination or suspension are detailed in [Section 14.1](#), Criteria for Premature Termination or Suspension of the Study.

### **7.5.3 Individual Study Site Termination**

Study participation may be suspended or terminated at an individual study site for various reasons. Criteria and procedures for premature termination or suspension of a study site are detailed in [Section 14.2](#), Criteria for Premature Termination or Suspension of Study Sites and [Section 14.3](#), Procedures for Premature Termination or Suspension of the Study or Study Sites. If a study site has been suspended or terminated, prompt notification will be given to investigators, IRBs, and regulatory authorities in accordance with regulatory requirements.

## **7.6 Subject Completion and Subject Discontinuation**

### **7.6.1 Subject Completion**

A subject will be considered as having completed the study after completion of their final study visit (Visit 15/Week 24, Safety Follow-Up or Early Termination).

### **7.6.2 Temporary Interruption of Study Drug**

Subjects who temporarily interrupt their study drug (vadadustat or epoetin alfa) after receiving the first dose and prior to completion of the study, will continue with the study visits, safety assessments, and other activities as deemed applicable through Week 20, and will complete the 4-week Safety Follow-Up Period and the Visit 15/Week 24 assessments (see [Appendix A](#): Schedule of Activities).

During the study, a subject may interrupt study drug (vadadustat or epoetin alfa) for any of the following reasons:

- AE
- Missed dialysis visit (epoetin alfa arm)
- Investigator's discretion
- Rapid rise in Hb (defined as >1.0 g/dL in any 2-week period)
- Hb above 11.0 g/dL
- ESA use (vadadustat arm)

Unless contraindicated, treatment will be resumed whenever possible and assessed at every visit following study drug interruption.

### **7.6.3 Early Discontinuation from Study (Early Termination)**

Subjects who discontinue prematurely from the study will complete the End-of-Treatment (EOT) visit (Visit 14) assessments and will complete the Safety Follow-Up (Visit 15) 4 weeks after Visit 14.

Subjects may discontinue for any of the following reasons:

- AE
- Investigator's discretion
- Subject withdrawal of consent

- Lack of efficacy, defined as inadequate response to vadadustat or epoetin alfa in the investigator's opinion
- Lost to follow-up despite reasonable efforts by the investigator to locate the subject. Every reasonable effort is to be made to contact any subject lost to follow-up during the course of the study to complete study-related assessments, record outstanding data, and retrieve study drug.
- Death
- Other reasons (pregnancy, kidney transplantation, specific reasons to be documented by the investigator)

Subjects who undergo a solid organ (including kidney), hematopoietic stem cell, or bone marrow transplantation will have their study medication (vadadustat or epoetin alfa) permanently discontinued and will complete the End-of-Treatment (Visit 14) and Safety Follow-up (Visit 15) visit assessments.

See [Section 9.4](#), Study Medication Stopping Rules for additional details on the management of subjects with ALT and AST abnormalities.

## **8 STUDY DRUG AND TREATMENT OF SUBJECTS**

Subjects will receive either vadadustat or epoetin alfa according to the randomization assignments provided via the Interactive Web Response System (IWRS) (see [Section 8.4.1, Randomization](#)).

Both vadadustat and epoetin alfa will be used as open -label supplies. All study drug supplies will be kept in a temperature-controlled, locked facility, accessible only to authorized study personnel.

The investigator or designated study personnel will be responsible for preparing study drug for dispensing to the subject (Section 8.1, Epoetin Alfa and Section 8.2.2, Dispensing of Vadadustat) and for study drug supply accountability ([Section 8.3, Vadadustat Accountability and Destruction](#)).

### **8.1 Epoetin Alfa**

Epoetin alfa solution for IV injection in multi-dose vials (e.g., 20000 U/2 mL and 20000 U/1 mL) or in single-dose vials (e.g., 2000, 3000, 4000, and 10000 U/mL) will be provided by the sites in commercially-approved primary packaging and stored per the approved label.

### **8.2 Vadadustat**

#### **8.2.1 Supplies and Storage**

Vadadustat will be provided as 150 mg, white to off-white, round, bi-convex film-coated, debossed or non-debossed tablets for oral administration. The tablets will be packaged in high-density polyethylene bottles with child-resistant closures, polypropylene liner, and induction seal. Labeling will be in accordance with current Good Manufacturing Practices and local regulatory requirements.

Dose levels utilized in this study will include: 150 mg (1 tablet), 300 mg (2 tablets), 450 mg (3 tablets), 600 mg (4 tablets), 750 mg (5 tablets), and 900 mg (6 tablets) per day or TIW.

Vadadustat will be stored per the product label. Please consult the Pharmacy Manual for details on storage and managing temperature excursions.

#### **8.2.2 Dispensing of Vadadustat**

At Baseline/Day 1, subjects who are randomized to vadadustat treatment will be administered the first dose of vadadustat at the study site.

Thereafter, vadadustat will be taken once daily from Baseline/Day 1 to Week 12 and TIW from Weeks 12 to 20 if Week 12 criteria are met ([Section 8.4.5.2, Transition of Vadadustat Once Daily Dosing to TIW Dosing Regimen](#)). If the investigator determined criteria for Week 12 is not met, daily dosing will continue on an outpatient basis. Subjects who are randomized to the vadadustat treatment arm will be provided with up to 2 bottles of vadadustat. Each bottle of vadadustat will contain 100 tablets of vadadustat (150 mg/tablet). Subjects may take vadadustat with or without food and will be instructed to swallow the tablet(s) whole. Subjects will be instructed to take vadadustat at approximately the same time each day.

Subjects will be instructed to bring unused vadadustat and empty bottles to each study visit for product accountability. Subjects will be instructed to finish 1 bottle before opening a new bottle.

Empty bottles will be collected at the study visits. Previously dispensed bottles (whether opened or unopened) with remaining tablets may be re-dispensed to the subject during the dosing phase of the study.

Resupply of additional vadadustat at subsequent visits will be managed via the IWRS and will be dependent on the current dose level of vadadustat and the number of tablets remaining in the subject's current vadadustat supply at a given study visit.

### **8.3 Vadadustat Accountability and Destruction**

Drug accountability will be an ongoing process throughout the study. All vadadustat will be accounted for and any discrepancies explained. The investigator or designated study personnel are responsible for keeping accurate records of the clinical supplies received from the sponsor, all supplies retained in inventory at the study site, and study drug dispensed to or returned from each subject. Records will be maintained that accurately reflect the drug accountability of vadadustat at all times. An electronic Diary (eDiary) or paper dosing reminders will be utilized throughout the study to guide dosing for subjects in the vadadustat arm (see [Section 9.1.2, eDiary](#)).

Proper drug accountability includes, but is not limited to:

- Continuously monitoring expiration dates
- Frequently verifying that actual inventory matches documented inventory.
- Verifying that the log is completed for all vadadustat received and that all required fields are complete, accurate, and legible.

If any dispensing errors or discrepancies are discovered, the sponsor will be notified immediately.

During the study, the investigator will be notified of any expiry dates or retest date extensions of clinical study material. If an expiry date notification is received during the study, the study site will complete all instructions outlined in the notification, including segregation of expired clinical study material for return to the sponsor or its designee for destruction as specified by the sponsor.

Prior to study site closure and at appropriate intervals during the study, a representative from the sponsor will perform clinical study material accountability and reconciliation.

At the end of the study, the investigator will retain all original documentation regarding clinical study material accountability, return, and/or destruction, and copies will be sent to the sponsor.

All unused and/or partially used vadadustat or other study materials will be returned to the sponsor or destroyed at the study site, as specified by the sponsor. Appropriate records of the disposal will be documented and maintained. No unused vadadustat may be disposed of until fully accounted for by the sponsor's monitor (or designee). Empty containers may be disposed of according to local procedures.

## **8.4 Treatment of Subjects**

The aim of the study is to achieve and maintain Hb levels within the target range of 10.0 to 11.0 g/dL, inclusive, while targeting the middle of the range and minimizing excursions outside the target range.

### **8.4.1 Randomization**

#### Main Study:

Subjects will be randomized to either a vadadustat treatment arm or epoetin alfa treatment arm. Randomization will be stratified by mean weekly epoetin alfa dose calculated over a period of 8 weeks prior to SV2:

- Low epoetin alfa dose group ( $\leq 90$  U/kg/week) or
- High epoetin alfa dose group ( $> 90$  to  $< 300$  U/kg/week)

In the low epoetin alfa dose group, subjects will be randomized in a 3:3:2 ratio to receive either an initial vadadustat daily dose of 450 mg (3 tablets) or 300 mg (2 tablets), or epoetin alfa.

In the high epoetin alfa dose group, subjects will be randomized in a 3:3:3:2 ratio to receive either an initial vadadustat daily dose of 600 mg (4 tablets), 450 mg (3 tablets) or 300 mg (2 tablets), or epoetin alfa.

#### ESA Hyporesponder Parallel Study:

Subjects will be randomized in a 1:1 ratio to receive either an initial vadadustat daily dose of 600 mg (4 tablets) or epoetin alfa.

**Note:** A subject may enter the washout period only after all eligibility criteria have been met. During the washout period, no epoetin alfa will be administered for 5 days in the Main study and 2 days in the ESA hyporesponder parallel study.

### **8.4.2 Blinding**

This is an open-label study and will not involve any blinding procedures.

### **8.4.3 Measurement of Hb Levels for Dose Adjustment Consideration**

Hb values will be measured by a central laboratory. Study drug treatment will aim to achieve and maintain Hb levels within the target range of 10.0 to 11.0 g/dL, inclusive, while targeting the middle of the range and minimizing excursions outside the target range. Hb will be monitored throughout the study to determine the dose of study drug (vadadustat or epoetin alfa) that subjects will receive (see [Section 8.4.6](#), Guidelines for Dose Adjustments). Hb levels can be measured more frequently based on investigator's clinical judgment.

In both the vadadustat and epoetin alfa arm, if dose adjustment is recommended based on Hb value and protocol-specified guidelines, dosing instructions can be provided to the subject over the telephone or at the next dialysis session at the study site (or dialysis center) or during an unscheduled site visit within 3 business days after receiving the Hb result from the central laboratory.

#### **8.4.4 Epoetin Alfa Dosing Regimen**

##### Epoetin alfa arm in both the Main study and ESA hyporesponder parallel study:

For subjects who are randomized to the epoetin alfa treatment arm, the initial dosing regimen in the study (starting from Baseline/Day 1) will be approximately the same weekly dose that they were receiving prior to randomization.

Epoetin alfa dose will be administered based on the subject's central laboratory Hb value and the approved epoetin alfa US PI for adult patients with CKD on dialysis.

From Baseline/Day 1 to Week 20, dose will be adjusted to achieve and maintain Hb levels within the target range of 10.0 and 11.0 g/dL, inclusive.

#### **8.4.5 Vadarustat Dosing Regimen and Guidelines for Dose Adjustment**

##### **8.4.5.1 Dosing Regimen for the Vadarustat Treatment Arm**

Subjects in the low epoetin alfa dose group randomized to vadarustat treatment will start at an initial dose of vadarustat 300 mg or 450 mg daily. Subjects in the high epoetin alfa dose group randomized to vadarustat treatment will receive an initial dose of 300, 450, or 600 mg daily. Subjects in the ESA hyporesponder parallel study randomized to vadarustat treatment will receive a starting dose of vadarustat 600 mg daily.

After completing the 12-week once daily dosing regimen, subjects randomized to vadarustat who meet criteria for switching from daily to TIW dosing will initiate TIW dosing at a starting dose 1 tablet greater (+150 mg) than the final dose in the daily dosing period (see Section 8.4.5.2, Transition of Vadarustat Once Daily Dosing to TIW Dosing Regimen).

Subjects who do not meet criteria for switching from daily to TIW dosing will remain on daily dosing. From Baseline/Day 1 to Week 20, dose will be adjusted to achieve and maintain Hb levels within the target range of 10.0 to 11.0 g/dL, inclusive.

##### **8.4.5.2 Transition of Vadarustat Once Daily Dosing to TIW Dosing Regimen**

All subjects randomized to vadarustat who complete 12 weeks of once daily dosing regimen **and** who meet all the Week 12 criteria below will be transitioned to a TIW vadarustat dosing regimen.

Week 12 Transition criteria:

- Vadarustat daily dose of 600 mg or lower at Week 12
- Hb within target range of 10.0 to 11.0 g/dL, inclusive, at Week 12 confirmed by central laboratory Hb value from Week 11 (11 weeks of treatment completed)
- No receipt of rescue therapy (ESA or RBC transfusion) for worsening of anemia due to CKD from Baseline/Day 1 to Week 12.
  - ESA or RBC transfusion prior to Week 12 for reasons unrelated to worsening of anemia due to CKD (e.g., surgery, gastrointestinal bleed, or inadvertent administration) is not considered rescue therapy

- No other reason, based on the investigator's clinical discretion that would make the subject not suitable for TIW dosing.

Selected subjects who meet Week 12 transition criteria will transition to the TIW vadadustat dosing regimen at the Week 12 visit. Subjects on 150, 300, 450, or 600 mg of vadadustat daily at the Week 12 visit will transition to an initial vadadustat TIW dose one tablet greater (+150 mg), i.e., 300, 450, 600, or 750 mg vadadustat TIW, respectively. Subjects will be instructed to take vadadustat on dialysis days.

After 2 weeks of treatment in the TIW vadadustat dosing regimen (at Week 14), subjects in any vadadustat TIW dosing arms who have a decline in Hb  $\geq 0.5$  g/dL will be eligible for a dose increase by 1 tablet, based on the investigator's clinical discretion.

Subjects who are not eligible to switch from daily vadadustat to TIW dosing at Week 12 will remain on daily dosing for the remainder of the study.

Subjects on TIW dosing may be converted back to vadadustat once daily dosing at the discretion of the investigator in the setting of inadequate Hb response. The starting daily dose after the switch from TIW to daily dosing will be based on the investigator's discretion after review of the subject's clinical status and dosing history, in particular, the daily dose previously administered to the subject prior to the transition to TIW dosing (Week 12). Subjects who switch from vadadustat TIW to daily dosing will continue once daily vadadustat until the end of the Treatment Period.

Subjects in the vadadustat arm will be guided for dosing compliance using an eDiary or through paper dosing reminders (see [Section 9.1.2, eDiary](#)).

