A 16-week, open-label, multicenter, Phase 2 trial evaluated vadadustat in 94 subjects receiving chronic hemodialysis previously maintained on epoetin alfa and IV iron form the 3 months prior to Screening (Study AKB-6548-CI-0011 [CI-0011]). Subjects were assigned to one of three vadadustat dose cohorts: 300 mg daily, 450 mg daily, or 450 mg three times a week (TIW). Dosing was fixed for the first 8 weeks; for the subsequent 8 weeks dose was adjusted from 150 to 600 mg according to Hb response based upon a dose adjustment algorithm. Sixty-nine of the 94 subjects completed the study. The primary endpoint was the mean Hb concentration change from pre-treatment average (Screening Visit 1, Screening Visit 2, and Baseline Visit) to mid-study (Weeks 7 to 8) and end-of-study (Weeks 15 to 16) and was analyzed using observed Hb values (no imputation for missing data). No statistically significant mean change in Hb from pre-treatment average was observed for either of the two time points for any of the three treatment groups.

Among subjects randomized to an initial dose of 300 mg daily, 450 mg daily, or 450 mg TIW, 0% (0 of 30), 3% (1 of 33), and 19% (6 of 31) of subjects withdrew from the study due to worsening anemia, respectively. In a sensitivity analysis using last observation carried forward (LOCF) for the primary efficacy endpoint, no significant mean change in Hb from pre-treatment levels was observed in the 300 mg daily dosing group. At Weeks 15 to 16, modest, statistically significant mean decreases were observed in the 450 mg daily and 450 mg TIW dosing groups.

In a post-hoc univariate analysis of baseline characteristics, higher pre-baseline epoetin alfa dose was associated with a decrease in mean Hb at Weeks 7 to 8 and Weeks 15 to 16 in the dosing cohorts. Subjects who discontinued the study due to worsening anemia had a higher mean pre-

baseline epoetin alfa dose compared with subjects who discontinued due to other reasons or subjects who completed the study.

Based on Phase 1 and Phase 2 study results, vadadustat appears to be a suitable candidate for continued development as a treatment for anemia in patients with CKD.

In the ongoing global Phase 3 and Japanese Phase 3 clinical studies, over 7000 subjects are planned to be treated with vadadustat or comparator.

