### 5.2 Secondary Objectives

- To assess the efficacy and safety of TIW dosing of vadadustat in selected hemodialysis subjects who have been successfully managed with daily dosing of vadadustat through Week 12
- To evaluate the PK/PD of daily and TIW dosing of vadadustat in hemodialysis subjects compared to epoetin alfa
- To assess the efficacy and safety of several dosing strategies of vadadustat compared to epoetin alfa during a 20-week Treatment Period in hemodialysis subjects

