#### 5.3.2 Key Secondary Endpoints

- Proportion of subjects with Hb values within the target range (10.0 to 11.0 g/dL, inclusive) at the primary evaluation period (Weeks 10 to 12)
- For subjects who transitioned to TIW vadadustat dosing, mean change in Hb from primary evaluation period (average Hb from Weeks 10 to 12) to the secondary evaluation period (average Hb from Weeks 18 to 20)

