#### **11.5 Missing Data**

It is expected that few subjects will discontinue Follow-Up. The reasons for any missing data will be summarized by treatment arm. Missing Hb values will be imputed using last observation carried forward (LOCF).

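### The TIW endpoints score Weeks 18 to 20 Hb for everyone who switched to TIW, including subjects returned to daily dosing for poor response, which pulls the TIW result toward stability

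*Protocol*

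**What the plan says.** One secondary objective in Protocol 5.2 is "To assess the efficacy and safety of TIW dosing of vadadustat in selected hemodialysis subjects" who did well on daily dosing through Week 12. Section 5.3.2 serves it with a key secondary endpoint, which begins "For subjects who transitioned to TIW vadadustat dosing, mean change in Hb from primary evaluation period (average Hb from Weeks 10 to 12"). The other end of that change is each subject's mean Hb over Weeks 18 to 20. Section 5.3.2.1 adds, for the same subjects, the proportion with Hb in the target range at Weeks 18 to 20. Neither definition requires that the subject still be on TIW at that time.

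Section 8.4.5.2 sets who switches and what may follow. Entry includes "Hb within target range of 10.0 to 11.0 g/dL, inclusive, at Week 12 confirmed by central laboratory Hb value from Week 11". After the switch, "Subjects on TIW dosing may be converted back to vadadustat once daily dosing at the discretion of the investigator" if Hb response is inadequate, and "Subjects who switch from vadadustat TIW to daily dosing will continue once daily vadadustat until the end of the Treatment Period".

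Section 11.5 states "Missing Hb values will be imputed using last observation carried forward (LOCF"). Section 11.6 makes the efficacy analyses descriptive. The protocol does not say how Hb after a return to daily dosing is treated in either TIW endpoint.

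**The concern.** Reversion is not a random change of regimen. It happens because Hb on TIW was judged inadequate, and it lasts through the window in which the endpoint is measured. The subjects for whom TIW worked least well are therefore the ones most likely to supply Hb values produced by a different regimen, and those values enter the TIW result unmarked. The error runs in one direction: the mean change moves toward zero and the in-range proportion moves up.

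At stake is the secondary objective on TIW efficacy. In the earlier hemodialysis study, among subjects started on 450 mg TIW, "19% (6 of 31) of subjects withdrew from the study due to worsening anemia" (Section 4.2). There, withdrawal was at least visible as missing data. In this trial a comparable subject may stay on study, take daily vadadustat and supply an observed Weeks 18 to 20 Hb. Neither an observed-data analysis nor a carried-forward one would then show that TIW had failed.

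**Working it through.** **What the plan gives.** No power, SD or effect size is stated; Section 11.1 calls the sample size exploratory. The allocation reproduces: 40 at 3:3:2 is 15/15/10; 55 at 3:3:3:2 is 15/15/15/10; 30 at 1:1 is 15/15. The total is 125, of whom 75 (Main) + 15 (hyporesponder) = 90 receive vadadustat. No figure in the protocol depends on the TIW endpoint, so the size of the problem has to be shown under assumptions.

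**Mean change.** Let
- f = share of transitioners who fail on TIW. Proxy: 6/31 = 19.4% (Section 4.2). Range 10% to 30%.
- D = Hb fall they would show at Weeks 18 to 20 had they stayed on TIW. Not in the documents; assumed 1.0 g/dL, range 0.5 to 1.5.
- r = share of that fall recovered on daily dosing by Weeks 18 to 20. Not in the documents; 0, 0.5 and 1 are shown.

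Assume that all failures revert and that everyone else has zero change. Then mean change = -f × D × (1 - r).

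| f | D (g/dL) | r = 0 (TIW fall) | r = 0.5 | r = 1 |
|---|---|---|---|---|
| 10% | 0.5 | -0.05 | -0.03 | 0.00 |
| 19.4% | 1.0 | -0.19 | -0.10 | 0.00 |
| 30% | 1.5 | -0.45 | -0.23 | 0.00 |

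The hidden amount is f × D × r. In the middle row it is 0.194 × 1.0 × 0.5 = 0.10 g/dL at half recovery and 0.19 g/dL at full recovery. It is smaller if only some failures revert.

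**In-range proportion.** Let p be the share in range among non-failures (assumed 70%). If reversion counts as non-response, the proportion is p × (1 - f) = 0.70 × (1 - 0.194) = 56.5%. If reverters are scored on their Weeks 18 to 20 Hb and are in range as often as the others, it is 70%. For f = 10% and 30% the first figure is 63% and 49%. With p at 60% or 80% and f = 19.4%, it is 48.4% against 60%, or 64.5% against 80%.

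**Starting value.** The Week 11 Hb that selects subjects is also one of the three visit values (Weeks 10, 11 and 12) in the starting average. Take subject means as normal with mean 10.2 g/dL and SD 0.8, and visit SD 0.6 (all assumed). One visit then has SD √(0.64 + 0.36) = 1.0. Given a value in 10.0 to 11.0, the expected Week 11 Hb is 0.276 above 10.2. The visit-error part is 0.276 × 0.36/1.0 = 0.099, and one third of that is 0.03 g/dL. It is 0.02 with visit SD 0.4 and zero if the population mean is 10.5. The effect is therefore below about 0.04 g/dL. In this calculation it makes the later change look slightly more negative, opposite to the reversion bias, and it vanishes if Week 11 is left out.

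**The case against.** **The strategy reading.** Following all transitioners whatever happens next is a legitimate summary of a TIW-first policy with daily dosing as fallback. This stands, and it is why the mean change need not be discarded. But Section 5.2 names the efficacy of TIW dosing, and the endpoint is not labelled as a strategy.

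**The size is assumed.** This also stands. The 19% comes from subjects switched straight from an ESA to 450 mg TIW, fixed for 8 weeks, and those six withdrew rather than reverted. Section 6.2 explains that this trial takes only daily-dosing successes, allows earlier increases and goes to 900 mg, so the rate may be lower.

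**Other places show failure.** ESA rescue and transfusion are separate endpoints, and Section 11.4 summarizes discontinuations with reasons. Return to daily dosing appears in neither.

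**The SAP may deal with it.** It is not at hand and could add an on-TIW analysis. The protocol nonetheless fixes the population and window of the endpoint itself.

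Three stronger readings are tempting and are not supported:
- *Carrying forward hides TIW failures by importing daily-period Hb.* Hb is scheduled at Weeks 13, 14, 16, 18 and 20, and early stoppers are to have the end-of-treatment visit with a blood count (Section 9.3.4; Appendix A, note c). A daily-period value is carried only if a subject is lost before the Week 13 draw with no later count. In the earlier study it was the carried-forward analysis that showed the decline, while observed data looked stable (Section 6.2).
- *Selection at Week 11 forces the in-range share to fall.* No listed endpoint compares transitioners' in-range share at Weeks 10 to 12 with that at Weeks 18 to 20.
- *The endpoint is invalid without an epoetin comparison.* The TIW objective, unlike the other two secondary objectives, does not claim one.

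**Conclusion.** The point holds on the text. The TIW set is defined by having switched, the outcome is Hb at Weeks 18 to 20 on any regimen, and reversion is triggered by poor response and lasts to the end of treatment. A subject who reverts before that window adds daily-dosing Hb to a TIW result.

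The direction is clear; the size is not known. With 19% failing, a 1.0 g/dL fall and all failures reverting, a TIW mean change of -0.19 g/dL would be reported as -0.10 or 0.00 at half or full recovery. Across the assumed ranges, the fall open to masking is 0.05 to 0.45 g/dL, and the whole of it is hidden only at full recovery. A reader might conclude that TIW failures will appear as stable Hb. The documents support only that they can, to a degree set by how many revert, when, and how far Hb recovers.

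The endpoint is descriptive and exploratory, with no test or decision rule attached. This is a cheap improvement to how it is defined and reported. The clinical rule that allows reversion is not in question.

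**What to change.** 1. **Section 5.3.2.1, TIW in-range proportion.** Count any of the following after Week 12 as non-response: return to daily dosing, rescue for worsening anemia, or discontinuation of study drug.
2. **Section 5.3.2, TIW mean change.** Keep the all-transitioners result and label it as the outcome of a TIW-first strategy. Report beside it the number and timing of reversions, and a supportive summary in which each reverter keeps the last Hb measured on TIW. Do not use a summary that drops reverters, since that would remove the failures again. The last TIW Hb is itself selected for being low and may overstate the fall, so this summary is supportive only.
3. **Minor.** Give a supportive starting value from Weeks 10 and 12 without Week 11.

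Hb, dosing and rescue data are already collected, so the cost is protocol and SAP wording. The price is a less favourable TIW success rate: under the assumptions above, 56.5% in place of 70%.
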